1.2. Rationale for Performing the Study

The aim of the Novoglan-01 clinical trial is to conduct a scientific study in compliance with good clinical practice in order to confirm the safety, efficacy and tolerability of the Novoglan product as a conservative treatment for adult phimosis. This study is expected to provide evidence for the use of the Novoglan product as an alternative to steroid creams in the conservative treatment of adult phimosis and have the urological treatment guidelines for adult phimosis updated accordingly.

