4. STUDY DESIGN

4.1. Design

The Novoglan-01 clinical trial is an investigator-initiated, single arm, non-randomised, observational, prospective study.

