4.4. Endpoints

Primary Endpoints

Primary endpoint – Efficacy of the device demonstrated by the improvement in foreskin retraction as measured using the Kikiros-inspired phimosis assessment scale.

Secondary Endpoints

First secondary endpoint – Safety of the device as evidenced by the reporting of any adverse effect or complication as observed and noted by the clinical trial team during the participant's treatment.

Second secondary endpoint – Participant satisfaction with the treatment as confirmed by treatment tolerability reported by the participant with a standardised treatment tolerability questionnaire and improvement in quality of life post-treatment as assessed by a standardised quality of life questionnaire before and after treatment.

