6.3. Study Procedure Risks

The following risk assessment for the Novoglan-01 study was prepared using Trial Risk Assessment for the NSLHD Investigator-led/Collaborative Group Clinical Trials published by the NSW Department of Health, Version 2.0 dated April 2016 (on file at Platigo Solutions).

Additionally, all measures designed to reduce risks are presented in the **Novoglan-01 clinical trial Safety Plan** submitted for review together with the Study Protocol.

- Participant Journey

The participant journey is described above in section 6.2.

- Additional risks with participants' physical integrity and safety

The Novoglan-01 study involves a medical device that is currently listed on the Australian Therapeutics Goods registry under the reference #168962 as a Class 1 (non-sterile) device indicated for the treatment of phimosis in adults. Furthermore, the Novoglan product will be used as per indications in the device TGA listing during the Novoglan-01 clinical trial.

Despite the Novoglan product having been commercialised without any reported adverse event, the Novoglan product safety has never been scientifically analysed and it is therefore reasonable to consider the study risk as Type B or somewhat higher than that of standard of medical care for adult phimosis, the standard of care being either the use of steroid creams or circumcision.

- Safety monitoring of the trial and DSMC

The establishment of a Data Safety and Monitoring Committee (DSMC) is not considered being necessary in view of the Type B risk category of the Novoglan-01 clinical trial and the fact that the Novoglan product will be used as on male adults as per usage instructions described in the listing of the device with the TGA.

- Risks to participants' rights

Risks to participants rights in taking part to the Novoglan-01 study have been assessed and mitigation strategies developed to minimise these risks. The risks evaluated fall into 2 categories and are presented in the following table.

Risks to participants' rights – The consent process		
Risk	Concerns	Risk minimisation strategy
Consent procedure	Does the consent process allow sufficient time for participants to consider their decision and discuss it with third parties	
 • Specific training on the consent/assent process will be provided to the clinical team. • First study visit following participant enrolment will be scheduled at least 1 week following the enrollment visit.

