6.7. Randomisation Procedure

The Novoglan-01 study does not require randomisation. It is a single arm, observational, open label, prospective clinical trial on a cohort of 24 participants all undergoing the same treatment with a product listed as a Class 1 device by the Australian Therapeutics Goods Administration for the treatment of adult phimosis.

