7. OUTCOMES

7.1. Definition of Outcomes

The expected outcomes from the Novoglan-01 study are as follows.

- Confirmation of the ability of the Novoglan product to effectively relieve phimosis as measured by foreskin retraction before and after treatment against the Phimosis Measurement Scale used at Study Visit 1 and Final Study Visit.
- Confirmation of the safety of the Novoglan treatment as evidenced by the lack of any severe adverse effect or any complication during treatment.
- Confirmation of the satisfaction of participants with the Novoglan treatment as measured by improved quality of life measured by questionnaire filled in by the participants before and after treatment.
- Confirmation of the tolerability of the Novoglan treatment as measured by the treatment tolerability questionnaire filled in by the participants during the Final Study Visit.
- Confirmation of the Novoglan treatment as a valid conservative first line treatment alternative to steroid creams in adult males presenting with phimosis.

Additionally, the publication of the Novoglan-01 study results at urology conferences and in a peer review journal is likely to encourage a review of clinical recommendations in the treatment of adult phimosis. Phimosis treatment guidelines published by the British Association of Urological Surgeons (BAUS) discourage the manual stretching of the foreskin and recommend the use of steroid creams or circumcision. The professional guidelines from the BAUS also refer physicians to the guidelines published by the European Association of Urology (EAU) which address phimosis in the section dedicated to paediatric urology.

Assuming a positive outcome from the Novoglan-01 study that demonstrates the safety, efficacy and tolerability of the Novoglan product in adult phimosis, the aim would be to:

- Convince the phimosis treatment guidelines published by the Urology Society of Australian and New Zealand (USANZ), EAU or BAUS to include a section dedicated to the treatment of adult phimosis.
- Convince the phimosis treatment guidelines published by the USANZ, EAU or BAUS to list the Novoglan product as a recommended conservative treatment for adult phimosis

Finally, the publication of the Novoglan-01 study results is likely to position MQ Health as the centre of reference for adult phimosis treatment in Australia. It is also likely to stimulate similar studies in Australia and overseas.

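### Section 7.1 expects to confirm a first-line role against steroid creams, which a single-arm before/after cohort with unrestricted cream history cannot do

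*Protocol*

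**What the plan says.** Protocol Section 7.1 (Definition of Outcomes) has five bullets of expected outcomes. The last is "Confirmation of the Novoglan treatment as a valid conservative first line treatment alternative to steroid creams in adult males presenting with phimosis". Section 1.2 (Rationale) points the same way in softer terms: "This study is expected to provide evidence for the use of the Novoglan product as an alternative to steroid creams". The same sentence goes on to the updating of urological guidelines. Section 6.3 explains why creams are the relevant reference, "the standard of care being either the use of steroid creams or circumcision".

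The design is described in Section 4.1 as a "single arm, non-randomised, observational, prospective study". Section 6.7 describes a "cohort of 24 participants all undergoing the same treatment", and Section 13 confirms that it is open label. The primary endpoint in Section 4.4 is "Efficacy of the device demonstrated by the improvement in foreskin retraction as measured using the Kikiros-inspired phimosis assessment scale".

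The inclusion and exclusion criteria (5.1, 5.2) do not mention topical steroids, past or current. Section 6.2 collects medication history at enrolment. It records concomitant medication at enrolment, at both phone visits and at the final visit.

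**The concern.** The fifth bullet makes two claims beyond before/after change. One is a standing relative to steroid creams. The other is a place in the treatment sequence, namely first. Neither follows from observing that men improve while using the device. The first needs something to compare with. The second needs to be known for men who have not already been through the usual conservative treatment.

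What is at stake is the conclusion that the trial may draw. If the bullet stays, a favourable before/after result can be reported as having met a pre-stated outcome about creams, although nothing in the trial bears on creams. That matters more because Sections 1.2 and 7.1 both look ahead to guideline bodies.

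**Working it through.** No figure in the protocol decides this point, so the check sets the sections side by side.

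**1. What each expected outcome in 7.1 rests on.**

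| Expected outcome | Measurement named in the bullet |
|---|---|
| Relief of phimosis | Phimosis scale, Visit 1 and Final Study Visit |
| Safety | Severe adverse effects and complications |
| Satisfaction | Quality of life questionnaire, before and after |
| Tolerability | Tolerability questionnaire, Final Study Visit |
| First-line alternative to creams | None |

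Four of the five carry a measurement. Only the comparative one does not.

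**2. What standing against creams would need, and what is there.** It would need a concurrent cream group, or an external cream result fixed in advance together with a definition of success. A claim of being no worse would also need a margin.

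- Concurrent group: none (4.1, 6.7).
- External cream result: none stated.
- Definition of success or threshold: none. The endpoint in 4.4 is improvement on the scale.
- Margin: none.
- Sample size (8.1): the stated 29 reproduces as 24 × 1.2 = 28.8, rounded up. Dividing instead gives 24 / (1 − 0.20) = 30. Neither calculation contains a quantity about creams, and 8.1 states no cream rate or effect size.

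**3. What a first-line role would need, and what is there.** It would need results identifiable as coming from men who had not used creams. The only prior treatment that 5.2 excludes is prepuce surgery, with frenuloplasty allowed. No restriction or washout for creams is stated. Three kinds of men can therefore enter: those who have never used a cream, those whom a cream has failed, and those using one now. For the second group the device is by definition not first line.

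**4. Whether the statistical plan, which is not shown, could close the gap.** It could tabulate cream history or name an external benchmark. It could not create a comparator group or an eligibility rule, because these belong to the design that the protocol fixes.

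**5. Why no magnitude is computed.** A numerical illustration would need a responder proportion, a cream response rate and a proportion of men using a cream alongside the device. The documents give none of these, and the ordinal endpoint comes with no responder definition. Any such figure would rest wholly on invented counts.

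**The case against.** The best defence is that the bullet is an aspiration. It is headed as an expected outcome and appears neither in the objectives (3.1, 3.2) nor in the endpoints (4.4). The hypothesis in Section 2 says only that the device is an alternative conservative treatment that is safe, efficacious and well tolerated. Alternative can mean simply another option. The guideline aim later in 7.1 is conditional on a positive result and seeks listing as a recommended conservative treatment, not as first line. Much of this stands: the trial sets up no formal comparison, and none of its endpoints is invalidated. It does not rescue the bullet, which sits under a heading that defines outcomes, speaks of confirmation, and names both first line and steroid creams.

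A reader might infer several stronger points that the documents do not support:

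- **That a non-inferiority margin was wrongly omitted.** No superiority or non-inferiority claim is made anywhere, so the margin is absent because no comparison exists.
- **That Section 1.2 is equally wrong.** It says only that evidence is expected, and a single-arm study can provide some. It needs a clarifying sentence, not a retraction.
- **That the analysis ignores cream use and will credit cream effects to the device.** Section 8.2 is a summary of a separate statistical plan. It already lists medical history among its descriptive variables, although it does not name concomitant medication. A breakdown by cream use is ordinary content for that plan. No section says that any participant will use a cream during treatment.
- **That Section 6.7 contradicts possible cream use.** The phrase "all undergoing the same treatment" explains why there is no randomisation. It shows the lack of a comparator and nothing more.

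**Conclusion.** The fifth bullet of Section 7.1 is wrong as written. A single-arm, open-label before/after cohort of 24, with no cream comparator, reference rate or margin and no distinction by cream history at entry, can confirm neither standing against steroid creams nor a first-line role. This rests on the visible text of Sections 1.2, 4.1, 4.4, 5.1, 5.2, 6.7 and 7.1, and on no assumed rate.

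The reach is limited. One of five expected outcomes is affected. The estimate of before/after change, the safety record, and the quality of life and tolerability results stand as planned. The finding concerns what may be concluded. It does not show that results would be biased by a particular amount, and it does not fault the analysis. It is worth correcting before results are reported, because the correction costs almost nothing and the unsupported claim is the one closest to the stated guideline ambition.

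**What to change.** Delete the fifth bullet of Section 7.1, or limit it to the before/after change in phimosis grade and the tolerability seen in men using the device. Add one sentence to both 7.1 and 1.2 saying that the study makes no comparison with steroid creams.

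As an optional addition, not the correction of an error, describe recorded prior and concurrent topical steroid use beside the primary result, using the medication data that Section 6.2 already collects. With about 24 men the cells would be small, so this should be descriptive only. The statistical plan may already provide for it.

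The cost is an amendment of wording and a more modest stated claim. No change to eligibility, treatment, visits or sample size is needed or proposed.

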8. STATISTICAL CONSIDERATIONS

[name] in a Note-To-File dated 15 September 2020 has decided to appoint [name] as biostatistician to the Novoglan-01 study. The credentials of [name] as a staff member of Macquarie University will better address the requirement for a highly professional and experienced biostatistical analysis of the Novoglan-01 study results than what [name] could provide.

In view of the cohort size of 24 participants and in view of the single arm, observational nature of the Novoglan-01 study, it is reasonable to consider the statistical analysis of the Novoglan-01 study as relatively simple. It has been documented by the study biostatistician in a controlled document stored in the Trial Master File and entitled “**Novoglan-01 clinical study – Statistical Plan**”. This document is attached to the Novoglan-01 Protocol. The main points of this document are summarised as follows.

8.1. Sample Size or Power Calculation

A power calculation was performed to assess which sample size (N) was appropriate for the Novoglan-01 clinical trial. Calculations show that 29 participants must be recruited to reach N = 24, considering a potential drop-out rate of 20%.

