11.1.	Investigator Authorisation Procedure.....	21
11.2.	Participant Protection	21
12.	SAFETY	21
12.1.	Adverse Event Reporting.....	21
12.2.	Serious Adverse Event Reporting	22
12.3.	Data Safety and Monitoring Committee (DSMC)	23
12.4.	Early Termination	23
13.	BLINDING AND UNBLINDING.....	23
14.	CONFIDENTIALITY AND STORAGE AND ARCHIVING OF STUDY	23
15.	TRIAL SPONSORSHIP AND FINANCING.....	23
16.	INDEMNITY	24
17.	KEY REFERENCES.....	24
18.	APPENDICES.....	24

Summary

Study title:

Novoglan-01 clinical trial to confirm the safety, efficacy and tolerability of the Novoglan product in treating adult phimosis

Protocol version: 2.1

Objectives

Primary objective: Confirm the efficacy of the Novoglan product as measured by the improvement in foreskin retraction against a standardised scale.

Secondary objectives: Confirm the safety and satisfaction with treatment as assessed by quality of life improvement and treatment tolerability.

Study design

Single arm, observational prospective trial

Planned sample size

Single cohort of 24 participants

Selection criteria

Participants 18 years or older consulting the Macquarie University Hospital and Princess Alexandra Hospital Urology Clinics with symptoms of adult phimosis, inability to fully retract the foreskin accompanied with pain or discomfort and including participants with prior frenuloplasty or Balanitis Xerotica Obliterans.

Study procedure

Enrolment Visit – Participant meets with physician who confirms eligibility criteria, measures the degree of phimosis and enrolls the participant into the study.

Study Visit 1 – Participant meets with clinical trial nurse for phimosis measurement, to complete the Quality of Life questionnaire and receive training and Novoglan materials and documentation.

Study Visit 2 and 3 – By phone between the clinical trial nurse and the participant at Week 1 and Week 4 post Study Visit 1 to review treatment progress.

Final Study Visit – At 6 to 8 weeks following Study Visit 2, participant meets with clinical trial nurse to measure foreskin retraction, complete the treatment tolerability questionnaire and the quality of life questionnaire – End of participant study

Statistical considerations Sample size calculation - As described in Section 8.
Analysis plan – As described in Section 8.

Duration of the Study

Completion by February 2022 from study start in September 2019

PREAMBLE – Clinical trial contributors and contact details

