4.2. Expected Participant Numbers

The Novoglan-01 study is expected to enroll 24 participants.

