4.5. Centres

The Novoglan-01 study will be running at two sites of the Macquarie University Hospital Urology clinic, New South Wales and at the Urology clinic of Princess Alexandra Hospital, Queensland, and a total of 24 participants are expected to be enrolled into the study.

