9.4. Data Flow

The Case Report Forms, questionnaires and all other study documents relating to a particular participant will be provided blank and collected once completed in 12 ring binders, each corresponding to a particular participant. Additional ring-binders will be used should

the study cohort exceed 12 participants. These ring binders will be kept in a lockable cabinet at the trial site and constitute part of the Novoglan-01 Trial Master File.

The access to the Study Data is strictly limited to the research team which includes [name] and [name] as study investigators, [name] and [name] as study research nurses, [name] and [name] as study investigator assistants and [name] as study biostatistician. On conclusion of the study when 24 participants have been accrued and on advice from [name], [name] will collate all Participants Folders and transfer the required information from the Case Report Forms into an Excel Novoglan-01 study spreadsheet prepared and communicated to [name] by [name]. To ensure correct transfer of data, [name] will review the correctness of the data transfer information from the Participant Folders into the Excel Novoglan-01 study spreadsheet. On receipt of the Excel Novoglan-01 study spreadsheet, [name] will carry out the statistical analysis that concludes the Novoglan-01 study.

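### The protocol gives three recruitment figures (29, 24 and 12) that cannot be reconciled; if enrolment stops at 24, the N = 24 of the sample-size calculation is reached only with no loss after Visit 1

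*Protocol*

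**What the plan says.** Section 8.1 separates the number recruited from the number remaining: "Calculations show that 29 participants must be recruited to reach N = 24, considering a potential drop-out rate of 20" per cent. On that wording 29 is the recruitment target and 24 is what is left after loss.

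Elsewhere 24 appears at the point of entry:

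- Section 4.2: "The Novoglan-01 study is expected to enroll 24 participants".
- Section 4.5, across the centres: "a total of 24 participants are expected to be enrolled into the study".
- Section 9.4, on when folders are collated for analysis: "On conclusion of the study when 24 participants have been accrued".
- The Summary, under planned sample size, has "Single cohort of 24 participants", and Section 6.7 has "prospective clinical trial on a cohort of 24 participants all undergoing the same treatment". Neither says whether these are enrolled or analysed.

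A third figure also appears. Section 12.4, in its list of reasons for early termination, treats enrolment as completed when a recruitment goal of 12 has been met. Section 9.4 has the forms "collected once completed in 12 ring binders, each corresponding to a particular participant", with more binders to be added if the cohort goes above 12.

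Section 6.9 replaces participants who withdraw before Visit 1, when the device and training are given. It provides no replacement after that visit.

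**The concern.** One number, 24, serves both as the count after drop-out and as the count at entry. Both can be true only if nobody is lost without replacement, and Section 8.1 does not assume that. The primary endpoint compares phimosis at Visit 1 with phimosis at the Final Study Visit, so a participant lost between the two has no paired measurement.

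A site working from Sections 4.2, 4.5 and 9.4 could stop five short of the number that Section 8.1 calls necessary. A reader of Section 12.4 could regard recruitment as finished at half the cohort. The study is small and is intended to support a change in treatment guidelines, so the number entering the primary comparison should not depend on which section is followed.

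**Working it through.** **Inputs.** Number wanted after drop-out: 24 (Section 8.1). Drop-out: 20% (Section 8.1). Stated recruitment: 29 (8.1), 24 (4.2, 4.5, 9.4), 12 (12.4). Replacement: before Visit 1 only (6.9). Significance level, power and effect size: not given in the protocol.

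**Step 1: reproduce 29.** 24 x (1 + 0.20) = 28.8, rounded up to 29. The stated figure is therefore the multiplication shortcut.

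**Step 2: number needed to keep 24 after 20% loss.** 24 / (1 - 0.20) = 30. With 29 recruited, 29 x 0.80 = 23.2 are expected. The 29 would leave 24 only at a loss of 1 - 24/29 = 17.2%. The difference from 30 is one participant.

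**Step 3: expected evaluable number if enrolment stops at 24.** Because withdrawals before Visit 1 are replaced, 24 start treatment. With a proportion q lost after Visit 1, the expected number is 24 x (1 - q).

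- All of the 20% lost after Visit 1 (q = 0.20): 24 x 0.80 = 19.2.
- All of it lost before Visit 1 and replaced (q = 0): 24.

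Section 8.1 does not say when the 20% is expected to occur, so the documents support the range 19.2 to 24 and no single value within it.

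**Step 4: expected number at 12.** On the same reasoning, between 12 x 0.80 = 9.6 and 12.

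**Step 5: chance of at least 24 evaluable.** Taking the unfavourable end, with each participant independently having a 20% chance of loss after Visit 1 (binomial):

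| Starting treatment | Expected evaluable | P(at least 24) |
|---|---|---|
| 24 | 19.2 | 0.8^24 = 0.005 |
| 29 | 23.2 | 0.46 |
| 30 | 24.0 | 0.61 |

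For 24 starting treatment, the 95% range of the evaluable number is about 15 to 23.

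**Step 6: power, as illustration only.** Assume a two-sided 5% test, a normal approximation, and that N = 24 was chosen for 80% power. The standardised effect is then (1.96 + 0.84)/sqrt(24), and power at 19 is Phi(effect x sqrt(19) - 1.96), about 70%. Starting from 90% power, the result is about 82%. None of these design values is in the protocol.

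**The case against.** The best defence is that the wording outside Section 8.1 is loose and does not set a cap. Sections 4.2 and 4.5 speak of expected numbers. The Summary and Section 6.7 describe a cohort, which can be read as the analysed group. The word accrued in Section 9.4 is open to interpretation. The accrual plan in Section 6.4, 2 to 3 a month over 12 to 18 months, allows 2 x 12 = 24 to 3 x 18 = 54 participants, so nothing there prevents 29 or 30. The 20% is described only as a potential rate, and early withdrawals are replaced. The study is single-arm, and the inconsistency biases no estimate.

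Much of this stands, and it limits what can be claimed:

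- A reader might infer that the trial will end with about 19 evaluable participants. The documents do not support that as a forecast. It holds only if enrolment stops at 24 and the full 20% is lost after Visit 1.
- A reader might infer that every operational section closes at 24. Sections 12.4 and 9.4 also carry the figure 12.
- A reader might infer that the study is underpowered. The protocol gives no power, and Section 8.2 names an ordinal regression model, so the test behind Step 6 is itself an assumption.

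The defence does not remove the contradiction. Sections 4.2 and 4.5 do say enrolled, no section other than 8.1 mentions 29, and the goal of 12 fits neither figure. The Statistical Plan may supply the power inputs, but it cannot make the protocol's own enrolment figures agree.

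**Conclusion.** The inconsistency is real and lies within the protocol itself. Three recruitment figures (29, 24 and 12) coexist, and 24 is used both before and after drop-out. The material gap is the five participants between 29 and 24. The one-participant difference between 29 and 30 is a side note and would not justify a finding alone.

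If enrolment stops at 24, the expected evaluable number is between 19.2 and 24, and N = 24 is reached only with no loss after Visit 1. If Section 12.4 were followed, as few as 9.6 would be expected. These results rest on the protocol's 20% rate, on replacement only before Visit 1, and on evaluable meaning that both phimosis measurements are available. The size of any loss of power cannot be stated from the protocol.

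**What to change.** Define 24 once, as either enrolled or evaluable, and use a single recruitment figure in the Summary and Sections 4.2, 4.5, 6.7, 8.1, 9.4 and 12.4.

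- **Without extra patients:** keep 24 enrolled. Restate Section 8.1 as about 19 evaluable if 20% are lost after Visit 1, and restate the power or precision in the Statistical Plan for that number. The cost is wording and a less favourable planning figure.
- **If 24 evaluable is kept as the target:** put 30 as the recruitment figure in Section 8.1 and the other sections. This is six more than the 24 now expected, and within the accrual range in Section 6.4.

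In either case, remove the goal of 12 from Section 12.4, bring the binder count in Section 9.4 into line, and make the Section 9.4 trigger match the chosen definition. If 24 means evaluable, participants who drop out should not count towards it. Section 8.1 should also say whether its 20% includes withdrawals before Visit 1, since that decides where in the range the expected number falls.
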